4. STUDY DOCUMENTATION AND DATA COLLECTION

4.1 ELECTRONIC CASE REPORT FORMS (eCRFs)

Original data will be collected from each investigational site and recorded into a secure Electronic Data Capture (EDC) application hosted by MedNet Solutions, Minneapolis, Minnesota, and audited and monitored by BIOTRONIK.

Information from electronically delivered source data (e.g. programmers) will be captured and stored in a validated environment until the end of the study.

The investigator will be required to use his/her electronic signature to verify the content of the data reported in the eCRFs.

Patient follow-up is required for all subjects enrolled in this clinical registry. The follow-up visit date is based on the Corox BP LV lead implant date, and are to be used for:

CELESTIAL REGISTRY PROTOCOL

- Screening Visit
- Enrollment (7-180 days after Corox BP LV lead implant or lead revision)
- Medical History and Implant (at enrollment)
- Routine follow-ups (every 3-4 months for a CRT-D and every 6 months for a CRT-P, \pm 1 month)
- Unscheduled cardiac related physician or hospital visits
- Final 5 Year follow-up (\pm 1 month)
- All cause Adverse Events
- Study Exit
- Patient Non-Compliance

4.2 DATA QUALITY CONTROL

BIOTRONIK will monitor study data closely. At any time, reports can be generated on data completion and missing data by the sponsor and by approved research personnel at each investigational site. An EDC system will be used to track received and expected follow-up data and eCRFs for each participant. This system provides the capability to monitor the status, volume, and disposition of data as well as to identify data completed, due, overdue, and backlogged. In addition, all study data will undergo extensive automatic edit and plausibility checks which provide information to the investigational sites to help improve and maintain data quality control procedures designed to detect inaccuracies and inconsistencies.

4.3 PATIENT RETENTION

Although the CELESTIAL Study sample size has been calculated with a 10% patient attrition rate per year (50% in 5 years), patient retention in a 5 year study may pose additional, unforeseen challenges. Therefore, BIOTRONIK has provided additional tools in an effort to minimize the number of patients that are lost to follow-up. The EDC system includes an overview of each patient's follow-up schedule, including the tolerance windows for each follow-up. The EDC system also provides a patient follow-up scheduling tool in the form of a Visit Scheduler Report. This report allows research personnel to become alerted to and track all study patients that should be scheduled for upcoming follow-ups. Additionally, the EDC system will automatically provide a bi-weekly action item list to each site coordinator in the form of email, which includes all patients that are due for scheduling.

Finally, to ensure protocol and follow-up compliance at all participating investigational sites, BIOTRONIK monitors will conduct monitoring visits (see Section 7). Monitoring visits include a review of patients that may be lost to follow-up.

5. PATIENT CONSENT

Patient participation in this registry is voluntary. It is required that all patients sign an IRB approved Patient Information and Consent Form (ICF) prior to participation in the registry. Patient informed consent must be obtained before enrollment and any protocol related procedures. To assist with the consent process, BIOTRONIK will provide a template patient ICF to participating sites.

The investigator is required to inform the sponsor and the reviewing IRB within 5 days if any patient was not appropriately consented to participate in the registry. The sponsor is then required to report any failure to obtain patient consent to the FDA within 5 working days of learning of such an event.

6. CONFIDENTIALITY AND RISK ANALYSIS

6.1 PATIENT DATA CONFIDENTIALITY

All information sent to BIOTRONIK pertaining to each patient will be kept confidential at BIOTRONIK and is subject to FDA audit. Reports submitted to the physician or publications of registry results will not make any reference to patient names.

In order to verify the study data and ensure study integrity, monitors from BIOTRONIK, the FDA, and the reviewing Investigational Review Board (IRB) may review and/or copy the study records.

6.2 RISKS AND RISK MINIMIZATION

This is a post-approval registry conducted using legally marketed devices implanted according to their approved labeling. BIOTRONIK foresees no additional risks associated with this registry beyond those stated in the labeling for the respective pulse generators and leads.

7. MONITORING

7.1 SUMMARY

BIOTRONIK, Inc. is the "sponsor" of the clinical registry. A sponsor is defined as an entity that initiates but does not conduct a post-approval registry. BIOTRONIK's responsibility as the post-approval registry sponsor is to ensure protocol and regulatory compliance through periodic monitoring of the investigation. BIOTRONIK has determined that this clinical investigation is not a significant risk study, as it concerns only legally marketed devices that are used in accordance with approved labeling. However, BIOTRONIK requires IRB review and a Patient Information and Consent form for all after-market research.

CELESTIAL REGISTRY PROTOCOL

7.3 MONITORING

A monitor may visit the post-approval registry site periodically throughout the registry. The sponsor may also require the presence of personnel from BIOTRONIK at follow-up procedures outlined by this protocol in order to assist the investigator and other site personnel. During periodic monitoring visits, assessment of the study site will include the following:

- Completion and submission of the required eCRFs and other applicable registry documentation
- Continued acceptability of the facilities
- Adherence to the clinical protocol
- Adherence to the applicable FDA regulations regarding the obligations of the investigator and maintenance of records

7.4 REGISTRY COMPLETION

BIOTRONIK will notify the post-approval registry site upon completion or termination of the registry or of the investigator's participation. At the sponsor's request, an investigator will return any equipment and pertinent information in their possession. The sponsor will provide a final report to each investigational site as required by FDA regulations. After FDA has agreed to terminate this registry, BIOTRONIK personnel will conduct a registry closure visit. During this final visit, BIOTRONIK will verify records and ensure that the investigator understands any applicable regulatory requirements, including those related to record retention. The investigator must retain records related to the registry for a period of 2 years after the investigation is completed.

7.5 DEVIATION FROM THE INVESTIGATIONAL PLAN

The investigator is required to conduct this registry in accordance with the signed investigator agreement and clinical protocol. The investigator shall notify the sponsor and reviewing IRB in writing no later than 5 working days after any significant deviation from the post approval registry that has occurred to protect the life or physical well being of a subject in an emergency. Except in such emergency, prior approval by the sponsor is required for significant deviations from the post-approval registry.

BIOTRONIK categorizes protocol non-compliance instances as either violations or deviations. Both protocol violations and deviations will be reported to FDA in the form of progress reports as necessary.

Protocol violations are defined as instances where the protocol requirements and/or regulatory guidelines were not followed, and are generally more serious in nature. Protocol violations are considered to potentially affect the scientific soundness of the study and/or the rights, safety, or welfare of subjects. Protocol violations include, but are not limited to, failure to obtain consent and patient inclusion/exclusion violations. These violations will be reported to FDA in accordance with applicable regulatory timelines, and the site must notify the reviewing IRB. Protocol violations must also be reported to the sponsor via Case Report Forms.

Protocol deviations are deviations from the requirements of the protocol in such a manner whereby data may not be usable or is not available. Protocol deviations are less serious in nature and do not require IRB notification as long as they do not effect the rights, safety, or welfare of the registry patient. Protocol deviations from the post-approval registry must be reported to the sponsor via Electronic Data Capture.

7.6 ADVERSE EVENTS

The investigator will be required to assess the association of each reported adverse event to the implant procedure, implanted system including the generator, any lead, or the Corox BP LV lead. For each of these relationships, the investigators will indicate whether the Adverse Event is not related, related, possibly related, or unknown.

All Adverse Events will be adjudicated by the Clinical Events Committee (see Section 7.7 Clinical Events Committee). The Clinical Events Committee (CEC) will have the responsibility to adjudicate all Adverse Events into one of the following three final classifications: related, not related, or unknown.

CELESTIAL REGISTRY PROTOCOL

In evaluation of the two primary safety endpoints, the estimates of SAE rates will be based on the number of patients with at least one related SAE as a proportion of total patients with no SAEs, related SAEs, or unrelated SAEs. Patients with a final adjudicated relatedness SAE classification of unknown will not have that individual unknown event contribute to or be included in the evaluation of primary safety endpoint 1 (overall complication-free rate). Patients with an adjudicated relatedness SAE classification of unknown for a specific type of individual SAE will not have that individual unknown event contribute to or be included in the evaluation of that type of SAE in primary safety endpoint 2. However, for purposes of Kaplan-Meier actuarial analyses, described in Section 2.7.1 Trend Analyses and Section 2.7.2 Missing Data, all SAE data on enrolled patients will be included, with follow-up time censored at the time of withdrawal or last completed follow-up visit.

For the purposes of this registry, an adverse event is considered to be implant related if any one of the following occurred:

- Coronary sinus dissection
- Coronary sinus perforation
- Pneumothorax
- Arrhythmias
- Cardiac Perforation with or without tamponade
- Non-healing pocket dehiscence requiring intervention
- Hematoma
- Other event requiring surgical intervention

Additionally, for purposes of this registry, an adverse event is considered to have occurred at any point if both of the following conditions are met:

Condition One (definitions can be found in Appendix A: Definition of Terms)

- Infection
- Cardiac perforation with or without tamponade
- Lead dislodgment
- High pacing threshold, intermittent capture, no lead capture
- Diaphragmatic/pectoral stimulation
- Lead impedance out of range, high impedance
- Lead impedance out of range, low impedance
- Lead related thrombosis
- Implant damage to lead (e.g. accidental cut to lead body during pocket revision, device replacement, etc.)
- Premature battery depletion
- Suspected lead failure
- Suspected generator failure
- Twiddler's Syndrome
- Lead undersensing or loss of sensing
- Skin erosion

Condition Two:

- Lead pacing polarity or pacing mode reprogrammed due to suspected lead failure
- Lead surgically repositioned
- Lead surgically explanted
- Lead surgically replaced
- Lead surgically abandoned
- Lead abandoned and pacing disabled
- Lead use continued based on medical judgment despite a known clinical performance issue
- Other lead related surgery performed

Note: If Condition One is corrected by reprogramming the pulse generator or lead (other than changing the polarity or pacing mode) and no other invasive action was taken, then the event will not be considered an adverse event and should not be reported. Similarly, programming changes in pacing polarity/vector or pacing mode that are not due to a suspected lead failure will likewise not be considered an adverse event and should not be reported. For example, electrical reprogramming of the pacing polarity to eliminate diaphragmatic stimulation will not be considered an adverse event.

The adverse events that the IRB considers reportable are dependent on the particular IRB. The protocol-defined Adverse Events not related to the Corox BP LV lead are detailed in Table 4. To avoid underreporting, BIOTRONIK recommends that, at a minimum, the investigational site reports the adverse events detailed above that occur during the CELESTIAL post approval study to BIOTRONIK and their IRB.

The investigational site should report the Adverse Event on the Adverse Event eCRF. Additionally, registry sites may report adverse events through MedWatch, FDA's adverse event reporting tool for market-released devices. As defined in BIOTRONIK's internal procedures, these adverse events may be reported by BIOTRONIK through manufacturer's MedWatch reports.

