2.6 REGISTRY SIZE

The estimated sample size requirement is based on both primary safety endpoints: a noninferiority comparison of the overall SAE free-rate to 92.5% at 5 years, excluding those SAEs listed in Table 4, and a non-powered, superiority comparison for those individual lead-related SAE to 1% at 5 years. The sample size for primary safety endpoint 1 was calculated based on the following assumptions:

Assumptions for primary safety endpoint 1

- Study Design: nonrandomized registry
- Type I error (alpha): 0.05 (one-sided for noninferiority)
- Statistical power: 80%
- Noninferiority delta: 5%
- Estimated SAE-Free Rate at 5 years: 92.5% for Corox BP LV Leads

For primary safety endpoint 1, a total of 240 evaluable subjects implanted with Corox BP LV leads would be required to demonstrate the noninferiority within 5% of a SAE free-rate of 92.5%. Assuming a 50% loss to follow-up rate over 5 years of follow-up, a total of 480 (240/0.5) subjects would be required to evaluate primary safety endpoint 1. Enrollment will seek to achieve 240 evaluable subjects for each of the Corox BP LV leads.

Assumptions for primary safety endpoint 2

- Estimated individual SAE rate at 5 years: 0.4%
- Allowable two-sided, upper 95% confidence bound: 1%

For primary safety endpoint 2, a total of 1000 subjects would be required to demonstrate a two-sided, upper 95% confidence bound of 1%, assuming an expected individual SAE rate of 0.4% (no more than 4 patients with an SAE out of 1000). Assuming a 50% loss to follow-up rate over 5 years (10% per year), a total of 2000 (1000/0.5) enrolled patients would be required for evaluation of primary safety endpoint 2.

The required sample sizes for the two primary safety endpoints are summarized in Table 5.

Table 5: Primary Safety Endpoints Sample Sizes

	Primary Safety Endpoint 1: Overall SAE free-rate	Primary Safety Endpoint 2: Individual SAE rates
Sample Size of Evaluable Patients	240	1000
Total with 50% Loss to Follow-Up over 5 years	480	2000

Due to the addition of the Corox OTW-L BP in the study, the total sample size was increased to 2500 to allow for sufficient enrollment of patients with this lead.

Study attrition

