2.7 DATA ANALYSIS

For both primary safety endpoints 1 and 2, pooling of data from the Corox OTW BP, Corox OTW-S BP, and Corox OTW-L BP LV leads will be justified as part of the final data analysis. The differences in outcomes for the Corox OTW BP, Corox OTW-S BP, and Corox OTW-L BP LV leads will be tested using an exact, Chi-square test. If no evidence is found of differences between the Corox OTW BP, Corox OTW-S BP, and Corox OTW-L BP LV leads ($p > 0.05$), then the results will be considered poolable for purposes of testing the protocol hypotheses associated with the two primary endpoints. If evidence of differences is found for a given endpoint, then the hypotheses for that endpoint will additionally be tested separately for each LV lead.

CELESTIAL REGISTRY PROTOCOL

Primary safety endpoint 1 will be evaluated by performing an exact, noninferiority test comparing a binomial proportion (overall SAE free-rate at 5 years) to 92.5%, with a noninferiority delta of 5%. Equivalently, the upper, one-sided 95% confidence bound for the absolute difference between the overall SAE free-rate and 92.5% must not exceed 5%.

The evaluation of primary safety endpoint 2 will be based on the exact, two-sided 95% confidence interval for the observed, individual SAE rates at 5 years. The upper bound of these 95% confidence intervals must be less than 1%.

The secondary endpoint of successful biventricular pacing will be summarized as a success rate at each of the scheduled CELESTIAL follow-up visits through 5 years post-enrollment, together with the associated exact, 95% confidence intervals.

The secondary endpoint of other SAEs at 5 years, which were excluded from the primary safety analyses (listed in Table 5), will also be summarized as SAE rates together with their associated exact, 95% confidence intervals.

The secondary endpoints of pacing threshold and impedance measurements for the Corox BP LV leads will be summarized at scheduled visits where they were evaluated, using standard measures, including means, standard deviations, medians, minimums, and maximums.

The secondary endpoint for overall incidence of serious adverse events that meet the primary endpoint 1 criteria will be evaluated separately for each Corox BP lead model using the criteria established for primary safety endpoint 1 and 2.

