2.7.2 Missing Data

The reasons for any missing data in the study will be documented. The sponsor will examine both missing-data patterns, which describe which values are observed and which are missing, and the missing-data mechanisms, which concern the relationship between missingness and the values of variables in the study data set [R.J.A. Little and D.B. Rubin, 2002, Statistical Analysis with Missing Data, 2nd edition, Wiley and Sons].

For evaluation of the primary study endpoints (safety endpoints 1 and 2), only patients who achieve 5 years of follow-up or have experienced a serious adverse event prior to 5 years will be included in the evaluation of the associated hypotheses. The secondary endpoint of other SAEs at 5 years, excluded from the primary safety analyses, will be analyzed in similar manner. There will be no imputation for these missing adverse event outcomes.

For purposes of Kaplan-Meier actuarial analyses, described in Section 2.7.1 Trend Analyses, all SAE data on enrolled patients will be included, with follow-up time censored at the time of withdrawal or last completed follow-up visit.

Secondary endpoints, which include successful biventricular pacing, pacing thresholds, sensing and impedance measurements will be analyzed in two ways. Initially, all available results will be summarized by scheduled visit through the 5 years of study follow-up. Afterwards, a last value carried forward (LVCF) will be used to estimate the values at the final 5-year follow-up evaluation.

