#### 3.2 PRIMARY ENDPOINT PER-PROTOCOL (PP) ANALYSIS POPULATION

The primary endpoint per-protocol (PP) population is a subset of the ITT population. The primary endpoint PP subjects have experienced a protocol defined primary endpoint AE or have a follow-up visit or system revision date completed 5 years post-implant (defined as a visit completed on or after 45 days prior to the 5 year post-implant date, 1781 days).

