### 5.2 PRIMARY ENDPOINT 2: SAFETY OF COROX BP LV LEADS PACING – INDIVIDUAL COMPLICATION RATES

Primary endpoint 2 will be evaluated based on the exact, two-sided 95% confidence interval for the observed, individual serious adverse event rates at 5 years. The upper bound of these 95% confidence intervals must be less than 1%. This endpoint will be evaluated using the subject population defined in section 3.2 Primary Endpoint Per-Protocol (PP) Analysis Population.

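### Read literally, the protocol counts early leavers with an unrelated SAE as five-year successes in both primary endpoints, while the SAP drops them; near its 1% limit, endpoint 2 can change verdict

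*Protocol*

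**What the plan says.** Three places together set the denominator of the primary endpoints.

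- **Protocol 2.7.2 (Missing Data)** says who is evaluable for both primary endpoints: "only patients who achieve 5 years of follow-up or have experienced a serious adverse event prior to 5 years will be included". It does not limit the SAE by relatedness or by whether it counts toward the endpoint.
- **Protocol 7.6 (Adverse Events)** defines the rate for both primary endpoints. The numerator is patients with at least one related SAE, taken "as a proportion of total patients with no SAEs, related SAEs, or unrelated SAEs". Patients with an unrelated SAE are therefore in the denominator only.
- **SAP 3.2** defines the primary per-protocol set as subjects who "have experienced a protocol defined primary endpoint AE or have a follow-up visit or system revision date completed 5 years post-implant", with day 1781 as the cut-off. SAP 5.1 uses this set for endpoint 1, and SAP 5.2 says the same for endpoint 2: "This endpoint will be evaluated using the subject population defined in section 3.2 Primary Endpoint Per-Protocol (PP) Analysis Population".

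Protocol 2.2 calls the Table 4 events SAEs and keeps them out of the primary endpoint. They include non-LV-lead death, with a prior-study range of 6.2–18.9%. Protocol 2.6 plans for up to 50% of patients to leave over five years, with death counted among the reasons.

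**The concern.** Consider a patient who leaves in year 1 after an unrelated SAE or a Table 4 SAE. Under the literal protocol wording the SAE makes the patient evaluable and does not count as an event, so the patient becomes a five-year success on one year of observation. Under the SAP the same patient is not in the analysis. The SAP does not mention the difference.

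The protocol version works in one direction. It adds partly observed patients as event-free and lowers the SAE rate, in a safety registry required by the FDA. Endpoint 2 is the more exposed of the two, because its planning case lies almost exactly on its 1% limit. A modest change in the denominator can then decide the result.

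**Working it through.** **Inputs.** Endpoint 2 passes if the exact two-sided 95% upper limit is below 1% (Protocol 2.7, SAP 5.2). The planning case is 4 events in 1000 evaluable, from 2000 enrolled (Protocol 2.6). Planned enrolment is 2500; with 50% leaving, about 1250 are evaluable. The number of early leavers with an unrelated SAE, *k*, is not in the documents.

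**Formula.** For *x* events in *n* patients, the Clopper-Pearson upper limit is U(x, n) = the 0.975 quantile of Beta(x + 1, n − x).

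**The plan's own figure.** U(4, 1000) = 1.021%. The smallest *n* at which 4 events give a limit below 1% is 1022. The stated 1000 therefore reproduces to within 2.2% (22/1000), but on the failing side.

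**Same events, two denominators.** The SAP denominator is *n*; the literal protocol denominator is *n + k*.

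| SAP n | Events | SAP limit | k added | Protocol n | Protocol limit |
|---|---|---|---|---|---|
| 1000 | 4 | 1.021% (fail) | 22 | 1022 | 0.999% (pass) |
| 1250 | 6 | 1.042% (fail) | 50 | 1300 | 1.002% (fail) |
| 1250 | 6 | 1.042% (fail) | 53 | 1303 | 0.9995% (pass) |
| 1250 | 6 | 1.042% (fail) | 155 | 1405 | 0.927% (pass) |
| 1250 | 6 | 1.042% (fail) | 472 | 1722 | 0.757% (pass) |

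The values k = 22 and k = 53 are the smallest that turn a fail into a pass. The values 155 and 472 assume that Table 4's range for non-LV-lead death applies to all enrolled and that those deaths fall before five years: 0.062 × 2500 = 155 and 0.189 × 2500 ≈ 472.

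**Most events of one type that still pass.** The smallest passing *n* is 1164 for 5 events, 1303 for 6, 1439 for 7, 1705 for 9 and 1835 for 10. Hence:
- SAP, n = 1250: at most 5 events.
- Protocol, n = 1405: at most 6 events.
- Protocol, n = 1722: at most 9 events.

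If *k* were only 2% of enrolled (50 patients), the maximum would stay at 5.

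**Endpoint 1.** At the one-sided 5% level against 87.5% event-free, up to 107 events in 1000 or 136 in 1250 pass (104 and 133 if the limit is taken from a two-sided 95% interval). The planned 7.5% gives 75 in 1000 or about 94 in 1250. Both pass on the SAP denominator, and a larger protocol denominator only lowers the rate.

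**The case against.** The strongest reply is that 2.7.2 meant endpoint SAEs all along. The sentence concerns the hypotheses of the two primary endpoints. The section then says that the SAEs excluded from those endpoints are handled in a similar way, and that missing outcomes are not imputed. Calling a year-1 leaver a five-year success would be imputation in effect. The 7.6 sentence, for its part, mainly explains how relatedness classes are treated. It has to name unrelated SAEs because patients who complete five years can have them, and taken alone it would also admit every early leaver with no SAE. So 2.7.2 must govern follow-up.

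Most of this stands. The 7.6 sentence alone proves nothing, and the narrower reading of 2.7.2 removes the main conflict with the SAP. But 2.7.2 does not state that reading, Protocol 2.2 uses the term SAE for Table 4 events, and nothing limits the 7.6 denominator to completers. A reader might infer that the protocol definitely intends to count these leavers as successes. The documents do not support that; they show wording that permits it.

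It also stands that the SAP names the stricter set for both endpoints, and that Protocol 2.7.1 and 2.7.2 already plan Kaplan-Meier curves on all enrolled patients for trend monitoring. Neither settles which denominator the protocol's hypothesis tests use.

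**Conclusion.** The two documents, as worded, give different denominators for both primary safety endpoints, and the literal protocol rule favours the lead. Whether this is a true conflict or loose drafting depends on how 2.7.2 is read.

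The consequence falls mainly on endpoint 2 and is conditional. It needs an event count near the limit and enough early leavers with an unrelated SAE: 22 in the 4-in-1000 case, 53 in the 6-in-1250 case. Under the assumed 6.2–18.9% of 2500 enrolled, the passing maximum moves from 5 events of one type to between 6 and 9. That range is borrowed from Table 4 and is not a forecast for this registry.

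Two stronger conclusions might be drawn and are not supported. One is that endpoint 2 is bound to flip: with 1250 evaluable and the planned 0.4%, there are 5 events, the upper limit is 0.931%, and both denominators pass. The other is that endpoint 1 is equally at risk: it shares the wording conflict, but at the planned 7.5% it passes either way.

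Nor is the SAP rule unbiased. It keeps early events and drops early leavers without one, which pushes rates upward. For endpoint 2 it also has a small version of the protocol's fault: one set serves every SAE type, so a patient who leaves early after one type counts as event-free for the others.

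**What to change.** - **Protocol 2.7.2:** replace the general reference to a serious adverse event with *a related SAE that counts toward primary endpoint 1 (for endpoint 2, of the type being tested)*.
- **Protocol 7.6:** keep the denominator sentence, since completers with unrelated SAEs belong in it, and add *among patients evaluable under Section 2.7.2*.
- **SAP 3.2:** adopt the same rule, including the type-specific condition for endpoint 2. SAP 3.3.1 to 3.3.3 restate the rule by lead model (3.3.2 without the primary-endpoint qualifier) and should follow.
- **Sensitivity analysis:** because the corrected rule still biases rates upward, report the five-year Kaplan-Meier estimate on all enrolled patients, censored at exit, beside the exact binomial test for both endpoints. Protocol 2.7.1 already plans these curves. Keeping the binomial test as primary preserves the basis of the sample size; making Kaplan-Meier primary would replace it.

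The cost is wording in both documents and one more reported estimate, with no new data. Reported SAE rates may look slightly less favourable than under the literal protocol wording.

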H₀: The serious adverse event-free rate (SAEFR) for the Corox BP LV Leads at 5 years post-enrollment is inferior to 92.5%

$$SAEFR + \delta \leq 92.5\%$$

H_a: The serious adverse event-free rate (SAEFR) for the Corox BP LV Leads at 5 year post-enrollment is not inferior to 92.5%

$$SAEFR + \delta > 92.5\%$$

CELESTIAL REGISTRY PROTOCOL

Where, (δ) is the clinically significant difference for establishing noninferiority. A rejection of the null hypothesis would indicate that the serious adverse event-free rate is not inferior to 92.5% within (δ).

2.3 PRIMARY ENDPOINT 2: SAFETY OF COROX BP LV LEADS – INDIVIDUAL COMPLICATION RATES

Each of the individual types of serious adverse events contributing to primary safety endpoint 1 will be evaluated separately in the following superiority hypotheses:

H_0 : The individual serious adverse event rate (SAEIndividual) for a given type of SAE for the Corox BP LV Leads at 5 years post-enrollment is equal to 1%

$$\text{SAEIndividual} = 1\%$$

H_a : The individual serious adverse event rate (SAEIndividual) for a given type of SAE for the Corox BP LV Leads at 5 years post-enrollment is not equal to 1%

$$\text{SAEIndividual} \neq 1\%$$

If the two-sided, 95% upper confidence bound is no more than 1% for individual serious adverse events, then the null hypothesis will be rejected for that SAE type.

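### SAEs finally adjudicated as unknown are left out of both primary safety tests, and no analysis shows what counting them would do; the rule can only favour a pass

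*Protocol*

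**What the plan says.** Protocol 7.6 has the Clinical Events Committee place every adverse event in "one of the following three final classifications: related, not related, or unknown". The SAE rate for both primary endpoints is the "number of patients with at least one related SAE as a proportion of total patients with no SAEs, related SAEs, or unrelated SAEs". That list omits anyone whose classification is unknown.

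For endpoint 1, a patient with an unknown SAE "will not have that individual unknown event contribute to or be included in the evaluation of primary safety endpoint 1". For endpoint 2, a patient with an unknown SAE of a given type "will not have that individual unknown event contribute to or be included in the evaluation of that type of SAE in primary safety endpoint 2". The same paragraph then says that Kaplan-Meier analyses will use all SAE data.

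Endpoint 2 is decided by an "exact, two-sided 95% confidence interval for the observed, individual SAE rates at 5 years"; SAP 5.2 states the criterion as "The upper bound of these 95% confidence intervals must be less than 1" percent. Endpoint 1 is an exact noninferiority test against 87.5% (92.5% less a 5% margin), with one-sided alpha 0.05 in the sample size section. SAP 3.2, 5.1 and 5.2 give no rule for unknown events and no sensitivity analysis that counts them. Neither document gives an expected share of unknowns, a limit on it, or a commitment to report the number.

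**The concern.** In a safety registry, missing information about causality is resolved in the device's favour. An event that meets every other endpoint criterion, but whose link to the lead could not be settled, is left out of the numerator. If some of these events were in truth caused by the lead, the observed rate is too low. No error runs the other way, because an unknown event never counts against the lead.

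Investigators may record an event as possibly related, but the committee has no such class, so some of these events may end as unknown. Protocol 7.8 asks for return of explanted leads and for death details only where available, so confirming evidence is not assured. Weaker documentation would then make both endpoints easier to meet. Endpoint 2 is most exposed to single events, because its outcome turns on a count of about three to five.

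**Working it through.** **Inputs.** Endpoint 2 null rate 1%, expected rate 0.4%, 1000 evaluable with no more than 4 events, attrition 50%, enrolment 2500 (Protocol 2.3 and 2.6). Evaluable at full enrolment: 2500 × 0.5 = 1250. Endpoint 1: 240 evaluable, limit 87.5%, one-sided alpha 0.05. Assumption, not in the documents: *u*, the share of truly lead-related events left as unknown. This is not the share of all SAEs classed unknown; if only some unknowns are truly related, the share of unknowns needed for a given effect is larger.

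**The plan's own figures.** The exact two-sided 95% upper limit is 1.02% for 4/1000 and 0.87% for 3/1000. Four events first pass at n = 1022, so the planned 1000 is reproduced to within about 2%, but read strictly only 3 events pass at 1000. At 1250, 5 events give 0.93% and 6 give 1.04%. For endpoint 1 at n = 240, passing needs at least 219 event-free patients: alpha 4.4%, power 80.7%. The planned 240 is reproduced.

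**Endpoint 2, simple binomial.** False-pass rate at a true 1% = P(X ≤ k), X ~ Binomial(n, 0.01 × (1 − u)). The nominal 2.5% is implied by the two-sided 95% interval; the documents do not state it.

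| n (k) | u = 0 | 5% | 10% | 20% | 30% | crosses 2.5% at |
|---|---|---|---|---|---|---|
| 1000 (3) | 1.0% | 1.5% | 2.1% | 4.2% | 8.1% | u = 12.6% |
| 1250 (5) | 1.4% | 2.2% | 3.2% | 6.6% | 13.1% | u = 6.9% |

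The crossing depends on where n falls between the discrete cut-offs. At n = 1025 (4 events) the rate is already 2.4% at u = 0 and crosses at u = 0.4%.

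**Endpoint 2, the plan's analysis set.** Protocol 2.7.2 and SAP 3.2 keep completers plus anyone with an event, so event-free dropouts leave the denominator and the observed rate rises. Assume 50% dropout spread evenly over 5 years. The fraction *c* of events seen before dropout is 1 − 0.5 × (mean event time ÷ 5 years): 0.75 for a constant hazard and 0.625 for a late-rising one (cumulative hazard proportional to t³). The expected observed rate is p·c / (p·c + 0.5(1 − p)).

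- Constant: 0.0075 / (0.0075 + 0.495) = 1.49%.
- Late-rising: 0.00625 / (0.00625 + 0.495) = 1.25%.

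Simulated false-pass rates at a true 1%:

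| Enrolled, hazard | u = 0 | 10% | 20% | 30% | 40% |
|---|---|---|---|---|---|
| 2000, constant | 0.03% | 0.1% | 0.3% | 0.9% | 2.6% |
| 2500, constant | 0.02% | 0.1% | 0.3% | 1.0% | 3.2% |
| 2000, late-rising | 0.2% | 0.5% | 1.3% | 3.1% | 6.8% |
| 2500, late-rising | 0.2% | 0.6% | 1.5% | 4.0% | 9.5% |

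The 2.5% level is crossed at roughly u = 25% to 40%.

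**Endpoint 1.** Simple binomial at a true 87.5%, P(X ≥ 219), X ~ Binomial(240, 1 − 0.125 × (1 − u)): 4.4%, 7.7% and 12.9% at u = 0, 5% and 10%. At n = 1250 (pass at 1114 event-free): 4.4%, 14.8% and 36.0%. The same analysis set offsets this. With p = 0.125 and the same *c* values as an approximation, the expected observed event rate is 0.09375 / (0.09375 + 0.4375) = 17.6%, or 0.078125 / (0.078125 + 0.4375) = 15.2%. It returns to 12.5% when the counted events fall to 0.0625, that is at u = 1 − 0.0625/0.09375 = 33% or u = 1 − 0.0625/0.078125 = 20% (unknown-only patients left out of the set).

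**The case against.** A reader might infer that the rule by itself pushes the endpoint 2 false-pass rate above 2.5%. The documents do not support that. They give no share of unknowns, and with none the rate is 1.0% to 1.4% at 1000 or 1250. At 1000 evaluable, 10% left unknown still gives only 2.1%. These figures also treat every event in *u* as truly lead-related, and the plan's analysis set inflates the observed rate and works against a false pass. All of this stands and limits the claim to what the rule can do. The offset is not a safeguard, however: it depends on how much dropout occurs and when events happen.

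A reader might also infer that unknown events vanish from view. They do not. Kaplan-Meier analyses use all SAE data, Protocol 2.7.1 compares those curves with the 92.5% and 99% targets and requires a report to FDA if they fall short, and Protocol 8.4 sends all reported adverse events to FDA every six months. But that is trend monitoring. The endpoints are decided by the binomial tests in SAP 5.1 and 5.2.

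The rule is pre-specified, and the committee is independent and blinded to site and patient identity. That guards against choosing the rule after the fact and against biased adjudication, but not against a rule that acts after adjudication and in one direction only. Counting every unknown as related errs the other way; in a safety test that is the conservative error, provided the events to be counted are defined.

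**Conclusion.** The concern holds as a statement about direction. Unknown events are removed from both primary tests, nothing in SAP 5.1 or 5.2 shows the result with them counted, and any truly related event among them moves the result only toward a pass. Inflation above the nominal level is possible but not established.

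For endpoint 2 it needs about 7% (n = 1250) or 13% (n = 1000) of truly related events left unknown under a simple binomial, and roughly 25% to 40% under the plan's analysis set with 50% even dropout, depending on event timing. Endpoint 1 has less slack in the simple binomial: at n = 240, 5% left unknown already exceeds its 5% alpha, before the same offset. All of this rests on an assumed *u* and assumed dropout and hazard patterns.

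One gap needs no assumption. The denominator in Protocol 7.6 omits patients whose only SAE is unknown, while SAP 3.2 admits any 5-year completer, so it is unclear whether such a patient counts as event-free or is excluded. For endpoint 2 the false-pass rates at n = 1000 and n = 1250 are the same to four decimals either way, but the rule should be stated.

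**What to change.** In Protocol 7.6 and SAP 5.1–5.2, count as related, in the endpoint tests, any SAE that otherwise meets the primary endpoint criteria (not a Table 4 exclusion) and whose relatedness to the Corox LV lead is finally classed as unknown. Report the result without these events as the sensitivity analysis. At minimum, pre-specify the unknowns-as-related analysis for both endpoints and state whether each conclusion holds under both versions.

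In either case, report the number of unknown events by SAE type, and state whether a patient whose only SAE is unknown stays in the denominator.

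The committee's classes are already collected, so no new data are needed. The minimum version costs SAP wording and one table; the full version also changes the protocol's endpoint rule. With unknowns counted, the simple-binomial false-pass rate for endpoint 2 is 1.0% at 1000 and 1.4% at 1250, both within 2.5%. The downside is a slightly less favourable SAE rate, because some of the counted events will not truly be lead-related.
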